3.4. Exclusion criteria

- (1) Transfer or automatic discharge within 2 weeks.
- (2) Patients with combined neonatal hemorrhagic diseases.
- (3) Newborns with severe malformations (such as congenital diaphragmatic hernia, umbilical protrusion, multiple malformations, etc.) or chromosomal abnormalities.
- (4) Incomplete and inaccurate hospitalization data.

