Project BA2023

study protocol and statistical analysis

plan

Title: Analyses of Anemia Risk Factors and Prognosis in VLBW Infants.

Study center

Shenzhen Bao'an Women's and Children's Hospital (ShenzhenBMCHH)

Shenzhen Longhua Women's and Children's Hospital

Time frame

Study Start: March 1, 2023

Study Completion: March 24, 2024

1. Background

Preterm infants (accounts for 9.9% of newborn infants in 2020) are born with immature organs and immune system[1]. Especially, 4% of them are extremely preterm infants with a gestational age of less than 28 weeks[2]. In recent years, the treatment and management of extremely preterm infants has become the main task of NICU. Moreover, the morbidity rate for extremely premature infants around the world has been rising annually. These vulnerable patients are prone to various complications. Anemia is one of the most common complications that occur during hospitalization in these infants[3]. Therefore, According to a survey by the Canadian Neonatal Network (CNN), over 75% of extremely preterm infants receive at least one blood transfusion treatment during hospitalization[4], and WhyteRK et al.[5] even pointed out that over 90% of extremely preterm infants require blood transfusion treatment during hospitalization. Most of the recipients of blood transfusions are caused by anemia, indicating a very high incidence and severity of anemia in these immature infants. Anemia of prematurity (AOP) can cause a series of adverse consequences such as apnoea, prolonged mechanical ventilation, prolonged hospital stay, necrotizing enterocolitis (NEC) [6], retinopathy of prematurity (ROP) [7], infection, and extrauterine growth restriction (EUGR). It can be seen that anemia in premature infants, especially in extremely preterm infants, has a significant impact on their prognosis.

There is a lack of evidence regarding the relationship between blood hemoglobin level at birth and the neonatal morbidity and mortality of preterm infants despite the mode of delivery and prenatal infection. It remains unknown the impact of early anemia on the neonatal morbidity and mortality of extremely preterm infants[8]. With this study, We hope to demonstrate the relationship between anemia on admission to the neonatal intensive care unit (NICU) and the neonatal morbidity and mortality in extremely preterm infants.

2. Objective and hypotheses

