3.2. The method of study

This was a retrospective study on the maternal and infant clinical and electronic records. We analyzed the maternal and obstetrical data, demographics, as well as the neonatal morbidity and mortality diagnosed during hospitalization. The study was approved by the Ethics Committee of our institution.

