3.3. Inclusion criteria

Extremely preterm infants with admission age \leq 24 hours, hospital stay \geq 14 days, and gestational age less than 28 weeks were included.

Anemia of Premature (AOP):

- Within 2 weeks of birth, venous blood hemoglobin level (Hb) \leq 130g/L, capillary blood \leq 145g/L.
- Age 2 weeks to 1 month, Hb $<$ 110g/L.
- Age after one month, Hb $<$ 90g/L.

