3.6. Study outcomes

The study outcomes and endpoints are listed in Table 1.

[figure not shown]
Table 1. List of study outcomes and endpoints.

Outcomes	Endpoints
General information	
 ● Sex (male or female) ● Pregnancy mode (In vitro fertilization or not) ● Chorioamnionitis (Yes or not) ● GBS colonization (Yes or not) ● Early onset sepsis (Yes or not) ● Antenatal steroids (Yes or not) ● Delivery mode (natural delivery or cesarean section) ● Multiple births (Yes or not) ● Gestational age (weeks) ● Birth weight (grams) ● Mother's hemoglobin level before delivery ● Mother's HCT level before delivery
Neonatal morbidity and mortality	
 ● BPD ● ROP ● NEC ● Early onset sepsis ● Late onset sepsis ● EUGR ● IVH ● Death

4. Statistical analysis plan

Categorical variables were expressed as proportions n/N (%) and compared using the Chi-square (χ^2) test. Continuous variables were expressed as (mean \pm SD) or median and interquartile range (P25, P75), and compared using Student's t-test or a nonparametric test, as appropriate. Two-tailed p-values < 0.05 were considered statistically significant. A multivariate analysis by logistic regression was performed to evaluate predictors of neonatal morbidities. Statistical analyses were performed using IBM SPSS Statistics, version 20.

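### Transfer and automatic discharge after day 14 have no rule for death, so later deaths go unrecorded and the anemia-death comparison may be biased in either direction

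*Combined protocol and SAP*

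**What the plan says.** Three parts of the protocol decide which infants are in the cohort and when a death is seen.

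- **Entry.** Section 3.3 requires "hospital stay \geq 14 days", with admission in the first day of life and gestation below 28 weeks.
- **Exit.** Section 3.4, exclusion (1), removes "Transfer or automatic discharge within 2 weeks". No other exclusion mentions transfer or automatic discharge. Exclusion (4) reads "Incomplete and inaccurate hospitalization data" and is not defined further.
- **Outcome window.** Section 3.2 describes a retrospective review of records and analyses "the neonatal morbidity and mortality diagnosed during hospitalization". Table 1 in section 3.6 lists death under "Neonatal morbidity and mortality", with no time point, definition or rule for unknown vital status.

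The Background (section 1) gives as an aim "the relationship between anemia on admission to the neonatal intensive care unit (NICU) and the neonatal morbidity and mortality". Section 4 plans chi-square tests, t or nonparametric tests, and logistic regression for morbidities. It has no censoring or missing-outcome method. Section 3.5 names length of NICU stay among the variables collected, but not type of discharge.

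**The concern.** An infant who leaves by transfer or automatic discharge on, say, day 20 or day 30 passes every dated criterion. A death after that point lies outside the hospital record, and the plan describes no follow-up. In a two-by-two table of anemia against death, such an infant has no death to count.

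The uncovered period is long. The plan itself assesses BPD at 36 weeks corrected age, which an infant born before 28 weeks reaches more than (36 − 28) × 7 = 56 days after birth. The exit rule covers 14 days, at most 14/56 = 25% of that span.

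Two results are at stake: the mortality proportion, and the association of anemia with death that the Background sets out to show.

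**Working it through.** The documents give no sample size, death rate or count of late exits, so there is no planned figure to reproduce. The first step is textual. The later steps use assumed values and show only how the mechanism behaves.

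**1. Path through the criteria.** An infant leaving after day 14 satisfies section 3.3 on length of stay and is outside exclusion (1). Under section 3.2 only a death in hospital is captured. Nothing in Table 1 or section 4 treats this infant's vital status as unknown.

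**2. Mortality.** Let d be the recorded share of deaths, L the share leaving late by either route, and q the probability of death after leaving. If late leavers carry no death, the recorded share is d and the true share is d + L × q. With d = 10% assumed:

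| L | true share, q = 0.2 | true share, q = 0.9 |
|---|---|---|
| 0% | 10.0% | 10.0% |
| 5% | 11.0% | 14.5% |
| 10% | 12.0% | 19.0% |
| 15% | 13.0% | 23.5% |

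The shortfall L × q runs from 0.05 × 0.2 = 1 point to 0.15 × 0.9 = 13.5 points. It is zero if nobody leaves late or nobody dies afterwards.

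**3. Association.** Assume recorded deaths of 10% (anemic) and 5% (non-anemic), with the same q in both groups. The recorded odds ratio is (0.10/0.90)/(0.05/0.95) = 2.11. The true value uses d + L × q in each group. For example, with late exits of 15% against 5% and q = 0.9, the shares are 0.235 and 0.095, and (0.235/0.765)/(0.095/0.905) = 2.93.

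| Late exits, anemic vs non-anemic | q = 0.2 | q = 0.5 | q = 0.9 |
|---|---|---|---|
| 5% vs 5% | 1.94 | 1.76 | 1.62 |
| 15% vs 5% | 2.34 | 2.62 | 2.93 |
| 5% vs 15% | 1.42 | 1.00 | 0.75 |

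The recorded 2.11 can be too high or too low. Equal exit rates do not remove the distortion.

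**4. What sets the direction.** Take 50 infants per group, with 5 recorded deaths in the anemic and 3 in the non-anemic (assumed). The recorded odds ratio is (5/45)/(3/47) = 1.74. Counting every late exit as a death gives:

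- exits 5 vs 1: (10/40)/(4/46) = 2.88
- exits 4 vs 3: (9/41)/(6/44) = 1.61
- exits 1 vs 5: (6/44)/(8/42) = 0.72

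In the second case anemic infants leave more often, yet the recorded value is too high. The direction depends on how much the hidden deaths multiply the odds of death in each group. Here the factor is (9/41)/(5/45) = 1.98 for the anemic and (6/44)/(3/47) = 2.14 for the non-anemic.

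**5. If exclusion (4) removed late leavers instead.** The reported share becomes d/(1 − L): 10.5%, 11.1% and 11.8% for L = 5%, 10% and 15%. Each is below the matching true range in step 2. The odds ratios become 2.12, 2.40 and 1.88 for the three rows of step 3. Only the second falls inside its true range. Dropping these infants does not in general recover the true value.

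**The case against.** The strongest reply is that in-hospital death is a legitimate endpoint and section 3.2 states that window. Under it, an infant who leaves alive is correctly recorded as not having died in hospital. This stands as a defence of the endpoint, and is a reason not to replace it with a composite. It does not cover reading the result as the relationship of anemia with mortality, because in-hospital death also depends on who leaves and when.

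A second reply is that the reach is limited. The formal hypothesis in section 2 concerns gestational age and birth weight, and the logistic model in section 4 names morbidities. This is fair. The death comparison rests on the Background aim, Table 1 and the group tests.

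Three stronger readings are tempting, and the documents do not support them:

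- **That the plan counts late leavers as survivors.** No such rule is written. It is an inference from in-hospital capture, and exclusion (4) might remove some of them. That would be another selection related to outcome, so it does not close the gap.
- **That late exits are concentrated among the sickest, or amount to withdrawal of care.** The documents give neither a count nor a reason for such exits, and no rationale for the 2-week limit.
- **That the association is pulled toward no effect if anemic infants leave more often.** The case of 4 against 3 exits shows that this is not general.

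**Conclusion.** The point holds as a gap in outcome capture. Infants who transfer out or leave by automatic discharge after day 14 remain eligible on the dated criteria and would have no death recorded. If any of them die after leaving, mortality is understated, and the anemia-death association may be biased in either direction.

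The size cannot be stated from the documents. The ranges above rest on assumed death shares, exit shares and risks of death after leaving, and the effect on mortality vanishes if there were no late exits or no deaths after them. The matter should be put right before the mortality results are interpreted. It does not touch the hypothesis about risk factors for anemia and transfusion.

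**What to change.** 1. From the records already under review, extract discharge type (planned, automatic, transfer, death) and day of life for every infant.
2. Report the number of late transfers and late automatic discharges by anemia group. If there are none, the concern ends there.
3. Keep death in hospital as the endpoint and label it so in Table 1. Do not present infants with a late transfer or automatic discharge as known survivors.
4. Add sensitivity analyses of the anemia-death comparison: death or automatic discharge after day 14 as a composite, and late transfers coded first all alive, then all dead. Simply removing late transfers from the denominator is not a substitute, since it can itself select on outcome.

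The cost is a few more chart items per infant and some extra table rows. Some infants counted as events in the composite may in fact have survived. Showing it beside in-hospital death makes that visible.

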3.5. General information

Several variables on mother, pregnancy, delivery, resuscitation, hematologic parameters including the Hct and Hb at admission, PRBC transfusions, use of vasopressor agents within the first 72 h of life, data on invasive and noninvasive respiratory support, neonatal morbidity and mortality, and length of NICU stay were collected and analyzed.

Care practices included antenatal steroid use, the use of antenatal magnesium sulfate, cesarean section, and delivery room resuscitation.

- Antenatal steroids: A full cycle of antenatal steroids was considered when at least 12 h had elapsed after the last dose of dexamethasone (four doses of 6 mg of dexamethasone given intramuscularly 12 h apart) administered to the mother [9].
- Antenatal magnesium sulfate was defined as the intravenous administration of magnesium sulfate to the mother during pregnancy at any time before delivery.
- Gestational age (GA) was determined according to the first day of the last menstrual period, an early prenatal ultrasound examination, and a physical examination of the infant after birth [10].
- Maternal chorioamnionitis was diagnosed clinically during pregnancy, labor, or delivery.
- Small for gestational age (SGA) was defined as a birth weight below the 10th percentile, based on the Fenton Growth Chart [11].
- Neonatal sepsis was diagnosed in the presence of clinical signs (fever; hypothermia; lethargy; tachypnea; apnea/bradycardia; cyanosis; and hypoglycemia not explained by other diagnosis), associated to at least two laboratory markers (thrombocytopenia; leukocytosis or leucopenia; C-reactive protein elevation; PCT; I/T) according to our National Program of Infection Control Guidelines [12]. Early-onset sepsis and late-onset sepsis were considered if diagnosed before and after the first 72 h of life, respectively.
- Intraventricular hemorrhage (IVH) was classified according to Volpe [13].

- Bronchopulmonary dysplasia (BPD) was defined according to the National Institute of Health [14]. For the analysis of this study, we considered BPD as the dependency for oxygen until 36 weeks of corrected age.
- Parenteral nutrition was used as soon as there was clinical stability, preferably since day one of life, starting with a volume of 70 ml/kg/day, with daily increments until 150 mg/kg/day by day seven of life. Incubator humidity is usually 70% during the first week.
- The modified criteria of Bell were used for the diagnosis and staging of necrotizing enterocolitis (NEC) [15].
- Staging of retinopathy of prematurity (ROP) was done according to the International Classification [16,17].

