Objective: To study the risk factors of anemia in different stages of extremely preterm infants and their impact on prognosis, which provide a certain evidence for improving the prognosis of these infants.

Hypothesis: Small gestational age and low birth weight are risk factors for anemia and receiving blood transfusion treatment in extremely preterm infants. The younger the gestational age and the lower the birth weight, the more severe the anemia, and the greater the likelihood of receiving blood transfusion treatment.

3. Study design

3.1. study subject

From January 1, 2020 to December 31, 2022, extremely preterm infants with a gestational age of less than 28 weeks were admitted to Bao'an Women's and Children's Hospital affiliated with Jinan University and Longhua District Women's and Children's Hospital.

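### Length of NICU stay is analysed with no planned adjustment for gestational age, which the plan expects to be lower in more anemic infants, so a crude comparison would be confounded

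*Combined protocol and SAP*

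**What the plan says.** Section 3.5 (General information) ends its list of variables with "and length of NICU stay were collected and analyzed". It gives no unit, no start or end point, and no rule for stays that end in death or transfer. Table 1 in Section 3.6 does not list stay among the outcomes; it does list GA, in weeks.

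Section 4 says that continuous variables are "compared using Student's t-test or a nonparametric test, as appropriate", with this criterion: "Two-tailed p-values < 0.05 were considered statistically significant". The only multivariable analysis is described in one sentence: "A multivariate analysis by logistic regression was performed to evaluate predictors of neonatal morbidities". Its covariates are not named, and no model is given for a continuous outcome.

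Two other places bear on the point. The hypothesis in Section 2 includes "The younger the gestational age and the lower the birth weight, the more severe the anemia". The Background in Section 1 counts "prolonged mechanical ventilation, prolonged hospital stay" among the adverse consequences of anemia of prematurity.

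**The concern.** Read together, these sections expect anemic infants to be less mature at birth, name longer stay as something anemia causes, and leave stay with a test that cannot take maturity into account. Infants enter the cohort within 24 hours of birth (Section 3.3). For those who go home from the unit, stay is therefore close to the time from birth until they are mature enough to leave. An infant born a week earlier may stay longer for that reason alone.

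At stake is the interpretation of one supporting result. If stay is compared crudely and the hypothesis about GA is true, a difference could be credited to anemia when GA produced some or all of it.

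**Working it through.** The documents give no sample size, SD, GA gap or length-of-stay figure, so there is no figure of the plan's own to reproduce. What follows is algebra plus an illustration.

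**Inputs from the documents.** Admission within 24 hours of birth and GA below 28 weeks (Section 3.3); unadjusted two-group test, two-sided 0.05 (Section 4).

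**Assumed inputs.** True anemia effect on stay: none. GA gap between groups: 0.5, 1.0 or 1.5 weeks. Fall in stay per extra week of GA (s): 7, 3.5 or 0 days. SD of stay: 21 days. Infants per group: 30, 50 or 100.

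**Step 1: the link between stay and GA.** For an infant discharged home, with PMA as postmenstrual age in weeks,

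stay in days ≈ 7 × (PMA at discharge − GA at birth).

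If PMA at discharge does not depend on GA, s = 7. If less mature infants also leave at a later PMA, s exceeds 7; if they leave at an earlier PMA, s is smaller.

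**Step 2: difference produced by GA alone.** D = s × GA gap.

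| s (days per week) | gap 0.5 | gap 1.0 | gap 1.5 |
|---|---|---|---|
| 7 | 3.5 days | 7 days | 10.5 days |
| 3.5 | 1.75 days | 3.5 days | 5.25 days |
| 0 | 0 | 0 | 0 |

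**Step 3: chance of p < 0.05 in favour of a longer stay.** Approximately Φ(D/SE − 1.96), with SE = 21 × √(2/n). For n = 50, SE = 21 × 0.2 = 4.2. A gap of 1 week at s = 7 gives 7/4.2 = 1.67, and Φ(−0.29) = 0.39. For s = 7:

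| n per group | gap 0.5 | gap 1.0 | gap 1.5 |
|---|---|---|---|
| 30 | 9% | 25% | 49% |
| 50 | 13% | 39% | 71% |
| 100 | 22% | 65% | 94% |

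At s = 3.5 and n = 50 the values are 6%, 13% and 24%.

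**Step 4: which analysis removes the bias.** Simulation with 1,000 data sets per scenario, 50 per group, GA SD 1 week, residual SD 20 days and no anemia effect. Entries are rejection rates at GA gaps of 0.5 / 1.0 / 1.5 weeks.

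| s | stay, unadjusted | PMA at discharge, unadjusted | stay, adjusted for GA |
|---|---|---|---|
| 7 | 13.5 / 37.1 / 66.7% | 4.2 / 4.8 / 4.7% | 5.2 / 4.1 / 4.2% |
| 3.5 | 6.6 / 12.1 / 26.7% | 6.8 / 13.6 / 23.6% | 5.1 / 4.8 / 4.2% |
| 0 | 4.7 / 4.6 / 5.5% | 10.8 / 40.0 / 67.8% | 4.1 / 3.6 / 6.6% |

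The simulation standard error at a true 5% is √(0.05 × 0.95/1000) = 0.7 percentage points. GA adjustment holds near 5% at every slope. Unadjusted PMA at discharge does so only at s = 7.

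**Step 5: why changing the scale is not the cure.** In days, 7 × PMA = stay + 7 × GA. In a linear model that contains anemia and GA, moving from stay to PMA in days raises the GA coefficient by 7 and leaves the anemia coefficient and its p-value unchanged. GA in the model does the work.

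**The case against.** The strongest reply is that the plan never commits to this comparison. Section 3.5 says only that stay was gathered and analysed. No sentence sets anemic against non-anemic infants on stay, and no unit is given. Table 1 omits it, the Background states the aim in terms of morbidity and mortality, and the hypothesis in Section 2 does not mention stay. This stands, and it makes the point one about a supporting variable. It does not dispose of it: Section 2 asks about the impact of anemia on prognosis, and the only method the plan offers for a continuous variable is crude.

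Three further objections also stand in part:

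- **Deaths and transfers.** The relation in Step 1 fails for stays that end in death or in transfer after 2 weeks. The 14-day minimum stay removes the earliest deaths, but later ones remain. If they fall mostly on the least mature infants, they shorten stay in that group and could reduce or reverse the bias.
- **Group sizes.** Equal groups have no source in the documents. With 100 infants split 85 to 15, SE = 21 × √(1/85 + 1/15) = 5.88, and a 7-day difference gives Φ(7/5.88 − 1.96) = 22% instead of 39%. The bias in days is unchanged.
- **Slope.** If stay does not vary with GA, there is no bias.

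A reader might infer more than the documents support:

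- That anemic infants stay longer merely because they were born earlier. This asserts a result. No data are shown, and GA may explain all, part or none of any difference.
- That the fault lies in measuring stay in days, so that PMA at discharge should replace it. Steps 4 and 5 show otherwise.
- That durations of respiratory support share the problem. Section 3.5 mentions data on such support but not durations or end dates.

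**Conclusion.** The concern holds as one of missing adjustment. Followed as written, the plan would give any comparison of stay between anemia groups no control for GA, although it expects GA to differ between them. Such a comparison may show a longer stay in anemic infants partly or wholly because of GA.

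For a GA gap of 0.5 to 1 week the spurious difference is about 3.5 to 7 days at 7 days per GA week, 1.75 to 3.5 days at half that slope, and none at zero slope. With 50 per group and an SD of 21 days, the chance of a falsely significant result at these gaps is about 13% to 39% at the full slope and 6% to 13% at half. All these inputs are assumptions, and they describe infants discharged home. Once deaths and later transfers are included, the direction of the bias is uncertain. Because stay is not a Table 1 outcome, the listed morbidity and mortality outcomes are not touched by this point.

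**What to change.** Amend Section 4 as follows:

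- Define length of NICU stay: its unit, start and end.
- Compare it between anemia groups in a regression that includes GA at birth, and take the anemia estimate and its confidence interval from that model.
- State how deaths and transfers after 2 weeks are handled. Two workable choices are to restrict the comparison to survivors discharged home, or to model time to discharge with death as a competing event and a stated rule for transfers.
- Report the unadjusted comparison as descriptive only.
- If PMA at discharge is wanted, show it alongside; it does not replace GA adjustment.

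The cost is SAP wording and one extra model. GA and death are already in Table 1; how each remaining stay ended would be read from the same hospital records. The apparent effect of anemia on stay may become smaller.

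### Length of NICU stay is analysed with no separate handling of deaths after day 14, so a stay ended by death counts as a short stay and biases the comparison if mortality differs between anaemia groups.

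*Combined protocol and SAP*

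**What the plan says.** Section 3.5 closes its list of collected variables with "length of NICU stay were collected and analyzed". Stay is therefore an analysed variable, although Table 1 in section 3.6 does not list it.

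Section 4 says that continuous variables are "compared using Student's t-test or a nonparametric test, as appropriate". It makes no exception for stay. The only model is for another purpose: "A multivariate analysis by logistic regression was performed to evaluate predictors of neonatal morbidities". The significance rule is general: "Two-tailed p-values < 0.05 were considered statistically significant".

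Deaths are part of the analysed cohort. Section 3.2 covers "neonatal morbidity and mortality diagnosed during hospitalization", and death is an endpoint in Table 1. Section 3.3 requires a stay of at least 14 days, which removes earlier deaths but not later ones. Section 3.4 excludes transfers and automatic discharges only when they occur within two weeks.

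The Background (section 1) includes "prolonged hospital stay" among the adverse consequences of anaemia of prematurity. The plan nowhere says how a stay that ended in death is to be counted.

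**The concern.** A NICU stay can end because the infant leaves alive or because the infant dies. A t-test or rank test on days of stay treats the two endings alike. An infant who dies on day 30 contributes 30 days, which looks better than a survivor's 85 days when a long stay is read as harm.

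The Background's stated aim is to relate anaemia on admission to morbidity and mortality. If anaemia raises mortality and also prolongs the stay of survivors, the two effects work against each other in this comparison. A real prolongation could then look small or absent. If survivors' stay does not differ at all, the group with more deaths can still show a statistically significant shorter stay.

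**Working it through.** The plan gives no figure to reproduce: no sample size, death rate, or mean or SD of stay. Every input below is an assumption chosen to show the mechanism.

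**Inputs (assumed)**
- Mean stay of survivors in the reference group B: M = 85 days; SD 20 days, roughly normal.
- Day of death among infants who die after day 14: uniform on days 14 to 60, so D = (14 + 60)/2 = 37.
- Mortality after day 14: pA in the anaemic group, pB in the other.
- True extra stay of survivors in group A: δ days.

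**Means**

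Mean stay is (1 - pA)(M + δ) + pA·D in group A and (1 - pB)·M + pB·D in group B. The difference, A minus B, is

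δ(1 - pA) - (pA - pB)(M - D), with M - D = 85 - 37 = 48.

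**Medians**

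All assumed deaths fall below the median, so each group's median is its survivor mean + 20·Φ⁻¹((0.5 - p)/(1 - p)).

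| Mortality A vs B | True δ | Mean difference (days) | Median difference (days) |
|---|---|---|---|
| 5% vs 5% | +7 | 7×0.95 - 0 = +6.65 | +7.0 |
| 8% vs 5% | +7 | 7×0.92 - 0.03×48 = 6.44 - 1.44 = +5.0 | +6.1 |
| 10% vs 3% | +7 | 7×0.90 - 0.07×48 = 6.30 - 3.36 = +2.9 | +5.0 |
| 15% vs 5% | +7 | 7×0.85 - 0.10×48 = 5.95 - 4.80 = +1.15 | +3.9 |
| 20% vs 5% | +7 | 7×0.80 - 0.15×48 = 5.60 - 7.20 = -1.6 | +1.9 |
| 15% vs 5% | 0 | 0 - 4.80 = -4.8 | -3.1 |

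The second term vanishes when pA = pB. With equal mortality there is no spurious difference, and a true difference in means is only scaled by (1 - p).

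**Rank test**

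With a true +7 days, the probability that a random infant in A stays longer than one in B is about 0.59 at 5% vs 5%, 0.53 at 15% vs 5% and 0.50 at 20% vs 5%. In the last case the rank test sees almost nothing.

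**Rejection rates by simulation (same inputs, two-sided 0.05)**
- No true difference, 100 per group, 5% vs 5%: about 0.05 for both tests, as it should be.
- No true difference, 100 per group, 10% vs 5%: about 0.12 (t-test) and 0.09 (Mann-Whitney).
- No true difference, 100 per group, 15% vs 5%: about 0.28 and 0.21.
- No true difference, 50 per group, 15% vs 5%: about 0.16 and 0.13.
- True +7 days, 100 per group: about 0.67 and 0.65 without deaths, falling to about 0.07 and 0.13 at 15% vs 5%.

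A different assumed shape (survivor stay 90 days with SD 25, deaths at 14 days plus an exponential time with mean 16) gives similar false-positive rates: 0.283 and 0.203 at 15% vs 5% with 100 per group.

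**The case against.** Stay is not a listed outcome. It appears in one catch-all sentence, Table 1 omits it, and the hypothesis in section 2 is about gestational age, birth weight, anaemia and transfusion. The Background's mention of long stay is one item in a general list. No section names a test for stay, and section 4 does not define the groups; both are inferred from a generic rule. This stands, and it limits the weight of the point. It does not remove it, because section 3.5 commits to analysing stay and section 4 offers no other method for a continuous variable.

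The 14-day minimum removes the earliest deaths, and later mortality may differ little between groups. This also stands: at 8% vs 5% the true +7 days still shows as +5.0, and at equal mortality the problem disappears.

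A reader might infer two stronger things. One is that the comparison will show anaemic infants leaving sooner, or even going home sooner. The documents do not support this. They give no mortality by group, they speak of NICU stay without saying that it ends at home, and a longer stay in survivors can offset the bias. The other is that the result will have the wrong sign. When survivors truly stay longer, reversal in the scenarios above occurs only for means and only at 20% vs 5%. The median difference stays positive there, at +1.9 days. Attenuation is the more general effect, and it affects the nonparametric option too.

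**Conclusion.** The point holds as a secondary issue that should be corrected. Followed as written, the plan counts a stay ended by death as a short stay, and this distorts the comparison of stay whenever mortality after day 14 differs between the groups. The direction of the distortion is known: towards a shorter stay in the group with more deaths. Its size is not, because the documents give no death rate, stay distribution or sample size.

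Under the assumed inputs, a true +7 days shrinks to between +5.0 and +1.15 days in mean for mortality gaps of 3 to 10 percentage points, and a gap of 10 points alone creates -4.8 days where there is no difference. Choosing the nonparametric test lessens the effect without curing it. The analyses of mortality and of the Table 1 morbidities are not touched by this point.

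**What to change.** Add to section 4 a rule for length of NICU stay, naming the groups compared. Either of two analyses would serve:

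1. Analyse time to live discharge from the NICU with death as a competing event, showing cumulative incidence by group.
2. Keep the nonparametric test, but rank infants who died as worse than the longest stay.

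In both cases, report median stay among infants discharged alive next to mortality, labelled as conditional on survival. State also how transfers and automatic discharges after two weeks are counted, since section 3.4 excludes only the earlier ones.

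The cost is a sentence or two in the SAP and a small amount of extra analysis. Stay and death are already collected; the mode and date of leaving the NICU should be confirmed as available in the records. The result is a little harder to describe than a mean stay, and the ranked version tests a composite of death and stay, so it must be described as such.
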